3.5.4. Electrocardiogram (ECG)

Electrocardiograms (ECGs) should be collected at times specified in the STUDY PROCEDURES section of this protocol.

The average of the triplicate readings collected at each assessment time will be calculated prior to analyzing each ECG parameter. If more than three readings are collected at one triplicate ECG assessment time, average across all readings will be calculated. If any of the three individual ECG tracings has a QTc value ≥ 500 msec, but the mean of the triplicates is not ≥ 500 msec, the data from the subject's individual tracing will be described in a safety section of the study report in order to place the ≥ 500 msec value in appropriate clinical context. However, values from individual tracings within triplicate measurements that are ≥ 500 msec will not be included in the categorical analysis unless the average from the triplicate measurements is also ≥ 500 msec. The mean measurement is reported.

Baseline will be the average of the triplicate ECG measurements collected on Day 0. Change and percent change from baseline will be calculated at each time point for each ECG parameter.

If not supplied, QTcF will be derived using Fridericia's heart rate correction formula:

$$QTcF = QT / (RR)^{1/3} \quad \text{where } RR = 60 \text{ bpm/HR (if not provided)}$$

If QTcB is collected, then it should be listed only.

Determine if there are any ECG data abnormalities of potential clinical concern as defined in Pfizer Data Standards. This data will be determined Overall, and separately for Period A and Period B.

3.5.5. Physical Examination

Physical Examination will be measured at times specified in the STUDY PROCEDURES section of the protocol.

3.5.6. Neurological Examination

Neurological Examination will be measured at times specified in the STUDY PROCEDURES section of the protocol.

3.5.7. Assessment of Suicidal Ideation and Behavior

3.5.7.1. Columbia Suicide Severity Rating Scale (C-SSRS)

The Columbia Suicide Severity Rating Scale (C-SSRS) is an interview based rating scale to systematically assess suicidal ideation and suicidal behavior. Versions are available for "lifetime/Past 12 months" and "since last evaluation". The "lifetime/Past 12 months" evaluation is done at screening, and the "since last evaluation" is done at all other time points.

The C-SSRS should be collected at times specified in the STUDY PROCEDURES section of this protocol by an appropriately trained clinical site staff member. The C-SSRS can also be administered at any time in the study at the discretion of the investigator based on any reasonable concern.

C-SSRS responses will be mapped to the Columbia Classification Algorithm of Suicide Assessment (C-CASA).

Table 3. C-SSRS Mapped to C-CASA - Suicidality Events and Codes

C-CASA Event Code	C-CASA Event	C-SSRS Response
1	Completed suicide	As captured in the safety database
2	Suicide attempt	“Yes” on “Actual Attempt”
3	Preparatory acts towards imminent suicidal behavior	“Yes” on any of the following: 
 • ”Aborted attempt”, or • “Interrupted attempt”, or • “Preparatory Acts or Behavior”
4	Suicidal ideation	“Yes” on any of the following: 
 • “Wish to be dead”, or • “Non-Specific Active Suicidal Thoughts”, or • “Active Suicidal Ideation with Any Methods (Not Plan) without Intent to Act”, or • “Active Suicidal Ideation with Some Intent to Act, without Specific Plan”, or • “Active Suicidal Ideation with Specific Plan and Intent”
7	Self-injurious behavior, no suicidal intent	“Yes” on “Has subject engaged in Non-suicidal Self-Injurious Behavior?”

The following 3 endpoints are key endpoints for suicidality data analysis and evaluation:

- Suicidal Behavior;
- Suicidal Ideation;
- Suicidal Behavior or Ideation.

Suicidal behavior: A subject is said to have suicidal behavior if the subject has experienced any of the following events (C-CASA event codes 1-3):

- Completed suicide;
- Suicide attempt; or
- Preparatory acts toward imminent suicidal behavior.

Suicidal ideation: Any observed suicidal ideation maps to a single C-CASA category. Depending on the scale used, more granularity of observed ideation (sub-categories of C-CASA category 4) may be displayed. The C-SSRS, for example, includes five ideation questions (that map to C-CASA category 4) with increasing severity.

Subjects with new onset suicidality: A subject will be considered to have a new onset of suicidality if the subject reported no ideation and no behavior at the baseline assessment (note that self-injurious behavior, no suicidal intent [C-CASA code 7] is not considered to be suicidal ideation or behavior) and reported any behavior or ideation post-baseline. Data observed at screening is not considered in the definition of new onset.

Subjects with worsening suicidality relative to baseline: A subject will be considered to have a worsening of suicidality if the subject moved to a lower numbered C-CASA category (observed in categories 1-4) than was reported at baseline. Movement within C-CASA categories 5-9 would not be considered worsening. In addition, worsening will be considered within the suicide ideation C-CASA category 4 if there is an increase in severity identified in the C-SSRS which captures additional granularity on suicide ideation. A subject who reports only ideation at baseline and who reports any behavior post-baseline is considered to have worsened. Data observed at screening is not considered in the definition of worsening.

Table 4 shows examples of new onset suicidality and worsening suicidality for C-SSRS after mapping to C-CASA.

Table 4. C-SSRS Mapped to C-CASA – Examples of Worsening/New Onset

New Onset		Worsening	
Baseline	Any post-baseline (or by visit)	Baseline	Any post-baseline (or by visit)
No ideation and no behavior	C-CASA code=4 (any ideation) or C-CASA code=1, 2, or 3 (any behavior)	Only C-CASA code=4 (Ideation only)	C-CASA code=3, 2, or 1 (any behavior)
		Lowest C-CASA code=4	C-CASA code=3, 2, or 1 (any behavior)
		Lowest C-CASA code=3	C-CASA code=2, or 1
		Lowest C-CASA code=2	C-CASA code=1

With the C-SSRS, worsening may also be observed within suicidal ideation. In this case, the order of suicidal ideations with increasing worsening is as follows: wish to be dead, non-specific active suicidal thoughts, active suicidal ideation with any methods (not plan) without intent to act, active suicidal ideation with some intent to act, without specific plan, and active suicidal ideation with specific plan and intent. All of these values will be considered worsening for reporting.

3.5.7.2. Mental Health Risk Assessment (MHRA)

At each suicidality assessment as per STUDY PROCEDURES, subjects felt to have significant suicidal ideation with actual plan and intent or suicidal behavior, must be evaluated by a clinician/mental health professional (MHP) skilled in the evaluation of suicidality in the subjects by virtue of training or experience (eg, psychiatrist, licensed clinical psychologist) who will determine if it is safe for the subject to participate/continue in the study. Specific criteria that indicate a need for such an assessment are:

- *Suicidal ideation associated with actual intent and/or plan in the past year; (a “YES” answer to C-SSRS questions 4 “some intent to act without specific plan” or 5 “specific plan and intent”).*
- *Previous history of suicide behaviors in the past 10 years (a “YES” answer to any of the suicidal behavior items of the C-SSRS with the behavior occurring in the past 10 years).*
- *In the investigators judgment a risk assessment or exclusion is warranted.*

When there is a positive response to any question on the C-SSRS, the investigator should determine whether an adverse event has occurred.

The PHQ-8 will be performed only at screening. Subjects that meet the Criterion PHQ-8 total score ≥ 15 indicate a need for risk assessment by MHP.

At the baseline visits (Screening, Day 0, or both), a risk assessment will be done by qualified staff at the clinical site to determine whether it is safe for the subject to be enrolled or to continue to participate in the study.

Subjects who respond “YES” to items 4, 5 or to any behavioral question of the C-SSRS at any time after the baseline visit (Screening or Day 0 (Randomization)) will be assessed by clinician/MHP to determine whether it is safe for the subject to continue in the study.

3.5.8. Questionnaire for Impulsive-Compulsive Disorders in Parkinson’s Disease – Rating Scale (QUIP-RS)

The Questionnaire for Impulsive-Compulsive Disorders (ICDs) in Parkinson’s Disease – Rating Scale (QUIP-RS) is a brief, patient reported outcome measure designed to assess the severity of symptoms of ICDs and related behaviors reported to occur in Parkinson’s disease.

The QUIP-RS has 4 primary questions pertaining to commonly reported thoughts, urges/desires, and behaviors associated with impulsive-compulsive disorder, each applied to the 4 impulsive-compulsive disorders (compulsive gambling, buying, eating, and sexual behavior) and 3 related disorders (medication use, punning, and hobbyism). It uses a 5-point Likert scale (score 0–4 for each question) to gauge the frequency of behaviors, and

instructs subjects to answer questions based on behaviors that occurred in the preceding 4 weeks (or any 4-week period in a designated time frame). Each question is anchored with the following five responses: Never (0), Rarely (1), Sometimes (2), Often (3), and Very Often (4). The scoring range for each item (ie, disorder) is 0-16. Scores will be computed for Gambling (0-16), Buying (0-16), Sex (0-16), Eating (0-16) and Total ICD score (0-64). The Total ICD score includes all 4 impulsive-compulsive disorders. Additionally, scores are computed for Hobbyism-punding (combined, 0-32), Compulsive medication use (0-16) and Total QUIP-RS score (0-112). The Total QUIP-RS score includes all 7 disorders. The higher score indicates a greater level of the Impulsive-Compulsive Disorder.

The general principle of allowing up to 20% of missing responses is applied. Therefore, the following subscores are set as missing if any of the pertaining 4 primary questions has a missing response: Each of the four ICDs (compulsive gambling, buying, eating and sexual behavior) and compulsive medication use. For the hobbyism-punding subscore that has 8 items, 1 missing response is allowed. For the Total ICD score that has 16 items, up to 3 missing responses are allowed. For the Total QUIP-RS score that has 28 items, up to 5 missing responses are allowed. This rule allows for the derivation of total scores even when some of the subscores are missing. With the presence of allowable missing responses, any sub or total will be calculated as follows:

$$(\text{Sum of the nonmissing item scores}) \times \frac{\text{total number of items}}{\text{number of nonmissing items}}$$

3.5.9. Physician Withdrawal Checklist (PWC-20)

The PWC-20 is a physician-completed, 20-item reliable and sensitive instrument for the assessment of benzodiazepine discontinuation symptoms. The PWC-20 is collected after the completion of study treatment and also at the first visit of follow-up.

Determine the number of subjects with each symptom present (eg, mild or higher severity) and categorize each subject by severity (eg, mild, moderate, and severe). Only non-missing items are considered in summary presentations, and will establish the denominator.

The total PWC-20 score is the sum of 20 item-scores and ranges between 0 and 60. The higher score indicates more frequent/severe symptoms. If more than 5 of the 20 individual items are missing then the total PWC-20 score will be set to missing.

If more than 5 items are missing, the total PWC-20 score is missing; otherwise, the total PWC-20 score will be imputed as follows: sum of the non-missing items X (total number of items)/ (number of items non-missing).

4. ANALYSIS SETS

Data for all subjects will be assessed to determine if subjects meet the criteria for inclusion in each analysis population prior to unblinding and releasing the database and classifications will be documented per standard operating procedures.

4.1. Full Analysis Set

The dataset used in the efficacy analyses will be the Full Analysis Set (FAS), consisting of all subjects randomized who receive at least 1 post-dose efficacy measurement (Hauser home diary). The FAS is the primary population for efficacy.

All subjects who receive at least 1 post-dose efficacy measurement will be classified according to their randomized treatment assignment. Randomized but took incorrect treatment subjects and randomized but not treated subjects will be reported under their randomized treatment group for all efficacy analyses. Treated but not randomized subjects will be excluded from the efficacy analyses since randomized treatment is missing.

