#### 2.4.2. Secondary Endpoints (Efficacy; Evaluated during the entire double-blind period)

Change from baseline in:

- Daily OFF time (hours).
- Daily ON time with troublesome dyskinesia (hours).
- Daily ON time without troublesome dyskinesia (hours).

- MDS - Unified Parkinson's Disease Rating Scale (MDS-UPDRS) Part III.
- MDS-UPDRS Parts I, II, IV, and total score.

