**Table 2. Proposed Titration Schemes for PF-06649751 and Placebo Doses**

Week/ Start Day of Dose Level	Treatment Group				
	Placebo	1 mg	3 mg	7 mg	15 mg
Week 1 / from Day 1	P	1 mg	1 mg	1 mg	1 mg
Week 2/ from Day 8	P	1 mg	3 mg	3 mg	3 mg
Week 3 / from Day 15	P	1 mg	3 mg	7 mg	7 mg
Weeks 4-15 / from Day 22	P	1 mg	3 mg	7 mg	15 mg

**Titration (Week 1 to Week 3):** No modifications to the upward titration of Study Medication can be made. Subjects who experience intolerable adverse events during titration will need to be discontinued from the study.

**Post Week 3 (Week 4 to Week 5):** For subjects who experience unacceptable new adverse events after having achieved the target dose (after Day 21) and deemed related to the dose increase, the dose of investigational product can be changed to the previous dose level (Week 3 dose level). This results in a dose reduction from 15 mg/day to 7 mg/day for the highest dose group, and no change in dose for the other dose groups in a blinded fashion. Only one dose modification of investigational product is permitted.

**L-Dopa Adjustment for Unacceptable Dopaminergic Side Effects (Week 1 to Week 15):** In the case of unacceptable dopaminergic side effects and following discussion with the Medical Monitor, the dose of L-Dopa may be reduced between Day 1 and Day 105 visit.

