- Register subject as Randomized in IWR system in order to obtain randomization number.
- Dispense Investigational Product. Subjects will begin PF-06649751 or placebo dosing the following morning (Day 1).
- Instruct subjects on continued daily dosing of PF-06649751 or placebo in accordance with randomized dose arm up-titration scheme (see [Table 2](#), Section 5.5.1, [Titration of PF-06649751](#)) and instruct subjects on proper dosing documentation.
- Instruct subjects on continued adjunct stable L-Dopa (open-label) administration.

#### 6.2.2. Dosing: Day 1 through Day 105

- Continued once daily dosing of PF-06649751 or placebo in accordance with randomized dose arm up-titration scheme (see [Table 2](#), Section 5.5.1, [Titration of PF-06649751](#)).
- Continued adjunct stable open-label L-Dopa administration (through Period B).

#### 6.2.3. Titration Period: Day 7

- Dosing compliance verification (Investigational product accountability and documentation) while subject is present to confirm reasons for missed/additional doses. **Based on blister card review and/or tablet count, any subject who is noted not to have taken at least 80% or has taken more than 120% of required doses at any scheduled visit during the study will be considered out of compliance and this must be recorded on the CRF and documented as a Medication Error on the CRF and the source documents.**
- Review and assess adverse events (AEs).
- Assessment of concomitant medications.

- Perform the Columbia Suicidality Severity Rating Scale (C-SSRS) “Since last evaluation”.
- Perform standard supine triplicate 12-lead electrocardiogram (ECG).
- Perform standard single supine and standing vitals (HR and blood pressure).
- Perform MDS-UPDRS Part III.
- Dispense OFF time diary, review instructions including requirement to wait until the next phone visit before completion of the diary.
- Dispense Investigational Product. Next immediate dose level of PF-06649751 or placebo will be taken the next morning.
- Instruct subjects on continued daily dosing of PF-06649751 or placebo in accordance with randomized dose arm up-titration scheme (see [Table 2](#), Section 5.5.1, [Titration of PF-06649751](#)).
- Instruct subjects on continued adjunct stable L-Dopa (open-label) administration.

#### 6.2.4. Titration Period: Day 14

In the case of a phone visit:

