## 9.2. Efficacy Analysis

The dataset used in the efficacy analyses will be the Full Analysis Set (FAS), consisting of all subjects who receive at least 1 post-dose efficacy measurement. Analyses may be repeated using a Per Protocol Set (PPS) as appropriate, which will exclude subjects who are major protocol deviators and subjects whose dosing compliance is less than 80%.

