6. ANALYSES AND SUMMARIES

Both the FAS and PPAS populations will be used in the analyses of the primary efficacy endpoint, with the FAS being primary. For all other efficacy endpoints, only the FAS analysis set will be utilized.

For all efficacy analyses and summaries (Sections 6.1, 6.2, 6.3 {except CCI [REDACTED]} and 6.4): All data collected for subjects consented under Protocol Amendment 2 prior to entering Period B will be included for modelling and summaries. Otherwise, only data collected through Week 10 (Period A) will be included for subjects who do not meet the above condition, and their data collected after Week 10 will be in listings only.

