6.2.2. MDS-UPDRS

Endpoints: MDS-UPDRS Parts I, II, III, IV, and total score

- Analysis time points: All Visits
- Analysis population (method of imputation for missing data): FAS (See [Sections 3.2.1 and 3.2.2](#)).
- Analysis methodology: Change from baseline will be analyzed using the MMRM Analysis (See [Section 5.2.2.1](#)) and Dose Response Analysis (MDS-UPDRS Part III @ Week 10 only, See [Section 5.2.2.2](#)).

- Supporting objective and Decision rule: Secondary Objective (See [Section 2.1.2](#)).

Reporting results:

[figure not shown]
- Raw data: The sample size, mean, standard deviation, median, minimum and maximum at baseline and post-baseline visits will be presented for each treatment arm.
- Change from baseline: The sample size, mean, standard deviation, median, minimum and maximum will be presented for each treatment arm. The point estimate, 90% confidence interval for the point estimate, difference from the placebo for each pair of treatment groups and the corresponding 90% confidence interval will be presented.

Figures

[figure not shown]
- Vertical bar chart of LS means and 90% confidence intervals at Week 10.
- Change from baseline time profile per MMRM for each treatment group.
- Empirical cumulative distribution function showing % of subjects with change from baseline \leq cutoff value at Week 10 by treatment group; (any drop outs are assigned to the left side of x axis).
- Dose response Emax model graph with the MMRM estimates (MDS-UPDRS Part III at Week 10 only).

CCI

CCI

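### The diary condition in SAP 4.1 removes some titration leavers with observed post-dose MDS-UPDRS scores from the MDS-UPDRS analyses, without a stated reason

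*SAP*

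**What the plan says.** Protocol Section 9.2 defines the FAS as "consisting of all subjects who receive at least 1 post-dose efficacy measurement" and names no instrument. Protocol Section 2.4.2 lists MDS-UPDRS Part III, and also "MDS-UPDRS Parts I, II, IV, and total score", among the secondary efficacy endpoints. On the protocol wording, a post-dose MDS-UPDRS score is enough to enter the FAS.

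The first paragraph of SAP Section 4.1 requires "at least 1 post-dose efficacy measurement (Hauser home diary". Its second paragraph repeats the criterion without the diary. SAP Section 6 then states: "For all other efficacy endpoints, only the FAS analysis set will be utilized". SAP Section 6.2.2 ("Endpoints: MDS-UPDRS Parts I, II, III, IV, and total score") names the FAS as its analysis population. The per-protocol set in SAP Section 4.2 is a subset of the FAS, so it restores nobody. The SAP version history lists no change to Section 4.1, and the SAP gives no reason for the diary condition.

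The visit schedule creates the gap. The Day 7 procedures (Protocol Section 6.2.3) include "Perform MDS-UPDRS Part III". The diary handed out that day comes with the "requirement to wait until the next phone visit before completion of the diary". Under Protocol Section 5.5.1, "Subjects who experience intolerable adverse events during titration will need to be discontinued from the study".

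**The concern.** A subject who attends Day 7 and then stops during titration, before keeping a diary, meets the protocol's FAS definition but not the SAP's. The observed Part III score is left out of every MDS-UPDRS analysis.

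The exclusion is not random with respect to treatment. Doses diverge between arms from Day 8 (Protocol Table 2). Protocol Section 1.4.2 reports that in the Phase 1b multiple-dose study most adverse events occurred during up-titration, with more nausea and vomiting at 15 and 25 mg than at 5 mg. The model in SAP Section 5.2.2.1 is likelihood-based and can use a subject's early visits under a missing-at-random assumption. Discarding those visits requires a stronger assumption and gains nothing. It also leaves two defensible readings of who belongs in the FAS, although SAP Section 4 wants membership settled before unblinding.

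**Working it through.** **1. The plan's figures.** Protocol Section 9.1 plans 32 evaluable subjects per arm and 10% loss: 32/0.9 = 35.6, so 36. The cohorts add to 54 + 144 = 198. By the allocation ratios, 15 mg has 36 + 18 = 54, placebo 18 + 18 = 36, and 1, 3 and 7 mg have 36 each. These agree with the protocol.

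**2. First post-dose measurement, by instrument.**
- Part III: Day 7 (Protocol Section 6.2.3).
- Diary: kept between Days 14 and 21 (Schedule of Activities, footnote 20; Protocol Section 6.2.4). SAP Section 3.1 has Week 3 as the first post-dose diary time point.
- Parts I, II and IV: Day 35 by the procedure lists in Protocol Section 6.2, unless collected at early termination (Protocol Section 6.6).

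The window for exclusion therefore opens at the Day 7 exam and closes when a first diary is completed.

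**3. Where early-termination exams go.** SAP Section 5.3 assigns them to the closest planned visit for that assessment, with ties to the later visit. If that visit already has a scheduled value, the scheduled value represents it.
- Part III, planned at Days 0, 7, 28, 35, 70 and 105: the midpoints are (0 + 7)/2 = 3.5 and (7 + 28)/2 = 17.5. Exams on Days 4 to 17 go to Week 1, where a scheduled Day 7 score prevails. Exams on Days 18 to 21 go to Week 4.
- Parts I, II and IV, planned at Days 0, 35, 70 and 105: the midpoint is (0 + 35)/2 = 17.5. Exams up to Day 17 go to Day 0, where baseline prevails. Exams on Days 18 to 21 go to Week 5.

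This uses the current procedure lists. The Document History records that Amendment 2 removed Part III exams at Weeks 2 and 3, so subjects seen under the earlier schedule could map differently.

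**4. What the diary condition costs.**
- Week 1 Part III scores of subjects who leave before a first diary. Through Day 7 every active arm is on 1 mg (Protocol Table 2).
- Early-termination exams from about Day 18 in subjects who still have no diary. This group is narrow because the diary window is already open.

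**5. How many.** The documents give no titration dropout rate. The nearest figure is the planned 10%: 0.10 × 198 = 19.8. The share falling between Day 7 and a first diary is an assumption:

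| Assumed share of the 10% | All 198 | 36-subject arm | 54-subject 15 mg arm |
|---|---|---|---|
| 25% | 5.0 | 0.9 | 1.4 |
| 50% | 9.9 | 1.8 | 2.7 |
| 100% | 19.8 | 3.6 | 5.4 |

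The last row is not a realistic case. The 10% also covers non-evaluable subjects and those who leave in Weeks 4 and 5, who would normally have a Week 3 diary.

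**The case against.** The strongest reply is that little is lost and nothing depends on it. Most recoverable scores are Week 1 Part III values on 1 mg. SAP Sections 5.1.1 and 5.1.2 attach the decision criteria to Week 10 OFF time, and MDS-UPDRS has no decision rule. Early-termination procedures may be left incomplete without counting as a deviation, and they include a diary review (Protocol Section 6.6), so some leavers may qualify for the FAS anyway. The SAP does not say whether a diary kept after dosing stopped counts as post-dose. All of this stands, and it is why the point is minor.

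Three stronger readings are tempting, and the documents do not support them.
- *The SAP breaches the protocol.* Protocol Section 9 lets the SAP modify the planned analyses and asks for an amendment only for major changes to the primary endpoint or its analysis. This is an unexplained narrowing, not a forbidden one.
- *All early-termination scores from Weeks 2 and 3, at 3 or 7 mg, are lost.* Under the mapping in SAP Section 5.3, most would not represent a visit even with a wider FAS, because a scheduled Day 7 or baseline value takes precedence up to Day 17.
- *The Phase 1b discontinuation rate bounds the loss.* Scaling 11/45 = 24.4% to 198 gives about 48. But 19 of those 45 subjects were in a 25 mg cohort, above this trial's top dose; the study was open-label; the count covers all adverse-event discontinuations; and the scaling applies the rate to placebo as well.

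**Conclusion.** The point holds at a modest size. SAP 4.1 excludes from the MDS-UPDRS analyses a group with observed post-dose scores, selected by tolerability, and gives no reason. The direction and size of any bias cannot be shown from the documents, and neither can the count, which is some fraction of about 20 subjects if early loss runs at the planned 10%.

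The main effect is on Week 1 Part III. The effect on Week 10 MDS-UPDRS is small, since these subjects have no Week 10 value and inform it only through the model's covariance. A reader might infer that the primary result is affected; essentially it is not, because a subject without a post-dose diary has no OFF-time change to contribute.

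This rests on the current procedure lists in Protocol Section 6.2, and on applying the first paragraph of SAP 4.1 literally rather than its second.

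**What to change.** In SAP Section 4.1, define the FAS per endpoint: for MDS-UPDRS, all randomized subjects with at least one post-dose MDS-UPDRS value. Keep the diary condition for the diary endpoints only, and make the section's two paragraphs agree. Alternatively, delete the parenthesis so that the SAP matches Protocol Section 9.2. In either case, state whether a diary kept after dosing stopped counts as post-dose.

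The cost is a sentence or two in the SAP before unblinding. It needs no new data, and the sample size and the primary analysis stay as they are.
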